Feedback is used to improve future sessions. Monthly, we prompt participants to rate the likelihood of future engagement. **The Intrinsic Motivation Inventory (IMI)** was developed from the perspective of Self Determination Theory to assess 7 dimensions of experience: Interest/Enjoyment, Perceived Competence, Effort/Importance, Pressure/Tension, and Choice[39,57–61]. We administer the 9 item short form of the IMI weekly to optimize instruction around high Perceived Competence and low Pressure/Tension[58,59] as well as explore relationships between adherence, motor effects, and IMI dimensions (including perceived benefit (Effort/Importance)). The Patient-Reported Outcome version of the **Common Terminology Criteria for Adverse Events v5 (PRO-CTCAE):** developed by NCI, is standard protocol in oncology to screen for signs of depression, anxiety, and apathy associated with cancer treatment or progression[62]. While not an outcome measure, we collect this staff-administered assessment per visit for adverse event screening, using the data to monitor and compare descriptive

statistics between groups. Changes in depression, anxiety, or apathy identified within check-ins, will be addressed.

c. *Within-Session Effects* Posture: will be captured before and after each Tango session in order to assess within-session change over time. A subset of **PROs**: (i.e., CIPN-20, BPI, and CRF) will be collected routinely before and after Tango training to allow analysis of within-session change. Finally, satisfaction with intervention will be collected after each session

Aim2: We will evaluate change in gait variability after 16 sessions of Tango (exp) vs HEX (control) (n=26 per group; 1:1 randomization). As secondary measures, we will analyze local and orbital dynamic stability (pre, post, and 1mo post-intervention), PROs (monthly), and falls incidence (weekly) following intervention completion. **Hypothesis:** At primary endpoint, members of the exp group will improve more relative to control group members in gait variability (i.e., stride-to-stride variability in speed).

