
Data collection: data may be collected using paper or electronic (e.g. MyCAP) versions of approved instruments.

Data storage: paper versions of source documentation will be kept in a locked cabinet within an OSU office that is accessible only to OSU clinical or research staff. Electronic data may be stored in a password protected spreadsheet or through RedCAP.

Interventions: training may be delivered in-person, via video conferencing, or via asynchronous instruction.

E. Internal Validity

All measures will be conducted by a researcher trained in the administration of the measure.

F. Data Analysis

Sample Size Justification: Preliminary data from our group was used to determine sample size requirements for this proposed randomized trial. **Aim 1:** Five cancer survivors with postural control deficits (RMSml>4.0mm) at baseline who participated in Tango practice improved RMSml from mean(SD) of 7.9(1.2) at baseline to 4.6(0.5) after 8 Tango sessions. Assuming more heterogeneity in our analysis sample, (SD=2.7 in control and intervention groups) we estimate Cohen's $d=1.22$. Thus we require an analysis sample of $n=14$ participants per group to provide 85% power at a 5% type I error rate. To account for anticipated drop-out and Aim2 analysis we will **enroll n=26 participants per group.** **Aim 2:** Preliminary data shows an Coefficient of Variation gait speed (CVspeed) SD of approximately 1.2 among survivors with neuropathy and postural deficits prior to Tango practice. With a sample size of $n=19$ per group (per Aim1) and this SD, we have 80% power to detect a difference of 1.32 ($d=1.1$). A cohort of 7 survivors with heterogeneous treatment progress (during and after chemotherapy exposure), not screened for or limited to those with postural control deficits, demonstrated a decrease in CVspeed ($p=0.003$) from 3.0(1.15) to 2.2(1.10) after ≤ 16 sessions of Tango practice ($d=0.711$). We will enroll **n=26 participants per group** to detect a reduction of this magnitude with 80% power.

Statistical Analysis Plan: Unless otherwise noted, all analyses will be performed on an intent-to-treat basis, and all hypothesis tests will be two-sided and at the 5% significance level. Enrolled participant characteristics will be summarized by assigned treatment groups.

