For **Aim 1**, a linear mixed effects model will be used to model postural sway (RMSml). Fixed effects will be included for time, treatment, treatment-by-time interactions, and concurrent medication use. Random effects for subjects will be used to account for correlation between observations from the same subject. The primary estimand will be a difference-in-difference representing the difference in mean RMSml change from baseline to week 16 between treatment groups. While we expect balance between the two groups due to randomization, we will adjust for potential confounders including baseline RMSml, age, body mass index, concurrent medications (e.g., duloxetine) and other variables if imbalance between groups occurs by chance. Similar analyses will be performed for the PROs sensory symptoms (CIPN-20), pain (BPI-SF), fatigue (0–10 Likert), quality of life (SF-36), and falls incidence following intervention completion. Finally, Pearson's R will be calculated to correlate postural control and balance outcomes, PROs, and future falls incidence.

For **Aim 2**, a similar analysis strategy will be used to compare biomechanical mobility between the two groups (linear mixed models; one-sided hypothesis test) as well as the correlation between biomechanical mobility outcomes, PROs, and falls incidence following intervention completion (Pearson's R).

Not all enrolled subjects will complete the intervention and have follow-up data. The linear mixed model analyses can use available data from all participants with at least one observation, regardless of whether or not they complete follow-up. We will compare the baseline characteristics of subjects who complete the study to those who drop out to assess the potential for attrition bias. A sensitivity analysis will be performed using multiple imputation to assess the impact drop-out has on study conclusions.

V. Funding

This project was funded, initially in Phase 1, through a 2015-16 Pelotonia Undergraduate Fellowship. We secured Phase 2 funding in 1R21AG068831 through the NIH National Institute of Aging (Note: this includes visit reimbursement for cancer survivors only).

VI. References

- [1] S.M. Monfort, X. Pan, R. Patrick, J. Singaravelu, C.L. Loprinzi, M.B. [name], A.M.W. Chaudhari, Natural history of postural instability in breast cancer patients treated with taxane-based chemotherapy: A pilot study, *Gait and Posture*. (2016). <https://doi.org/10.1016/j.gaitpost.2016.06.011>.

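### The two Aim 2 power statements rest on different, unlabelled bases: 1.32 with 80% power is the two-sided result for 14 per group, not 19, and 26 per group for d = 0.711 is a one-sided result with almost no room for drop-out

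*Combined protocol and SAP*

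**What the plan says.** All of this is in section IV.F, Data Analysis.

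- **Aim 1 sample size.** From d = 1.22: "Thus we require an analysis sample of $n=14$ participants per group to provide 85% power", at 5% type I error. Enrolment is then raised to 26 per group: "To account for anticipated drop-out and Aim2 analysis we will" enrol that number. No drop-out rate is given.
- **Aim 2, first statement.** The SD of CVspeed is about 1.2 in survivors with neuropathy and postural deficits. Then: "With a sample size of $n=19$ per group (per Aim1) and this SD, we have 80% power to detect a difference of 1.32", labelled d = 1.1.
- **Aim 2, second statement.** In seven survivors not screened for postural deficits, CVspeed fell from 3.0 (SD 1.15) to 2.2 (SD 1.10) with p = 0.003, labelled d = 0.711. The plan enrols 26 per group "to detect a reduction of this magnitude with 80% power".
- **Tests.** Unless otherwise noted, "all hypothesis tests will be two-sided and at the 5% significance level". The Aim 2 analysis is noted as an exception: "linear mixed models; one-sided hypothesis test". Its alpha is not restated.
- **Missing data.** The Statistical Analysis Plan expects that some participants will lack follow-up data.

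**The concern.** The first Aim 2 statement cites Aim 1 for a number that Aim 1 does not contain, and the power attached to it looks too low for 19 per group. The second looks too high for 26 per group under the plan's default two-sided test. The same 26 is also given two jobs: delivering 80% power for d = 0.711 and covering drop-out.

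Aim 2 has its own hypothesis and is cited as a reason for enrolling 26. A reader should be able to tell which test, analysed number and variance support that figure, and at present cannot.

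**Working it through.** **Method.** Two-sample t-test, 1:1, with n analysed per group. Power comes from the noncentral t distribution with 2n − 2 degrees of freedom and noncentrality d × √(n/2). Alpha is 5%; for the one-sided Aim 2 test this level is carried over from the general rule.

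**Aim 1, to confirm the method.** d = (7.9 − 4.6)/2.7 = 1.22. Two-sided power is 87.4% with 14 per group; 85% needs 13.1, so 14. The plan's figure reproduces.

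**Aim 2, first statement.** d = 1.32/1.2 = 1.1.

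| n per group | Test | Power for d = 1.1 | Smallest d at 80% power | × SD 1.2 |
|---|---|---|---|---|
| 14 | two-sided | 80.0% | 1.100 | 1.32 |
| 14 | one-sided | 88.3% | 0.965 | 1.16 |
| 19 | two-sided | 91.0% | 0.934 | 1.12 |
| 19 | one-sided | 95.4% | 0.822 | 0.99 |

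The stated pair (80%, 1.32) matches the first row exactly and neither row for 19.

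**Aim 2, second statement.** d = 0.8/√((1.15² + 1.10²)/2) = 0.8/1.125 = 0.711. 80% power needs 25.16 per group one-sided, so 26, and 32.04 two-sided, so 33. The loss levels below are assumptions, since the plan gives no rate.

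| Analysed per group | One-sided power | Two-sided power |
|---|---|---|
| 26 | 81.2% | 71.0% |
| 25 | 79.8% | 69.3% |
| 23 | 76.7% | 65.5% |
| 21 | 73.2% | 61.3% |
| 19 | 69.3% | 56.9% |

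So 26 is a one-sided figure, while 1.32 is two-sided. The SDs differ too: at the 1.2 quoted for the target population, 0.8 is d = 0.8/1.2 = 0.667, and 26 analysed gives 76.6% one-sided.

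**Is there a real shortfall?** The planned contrast is a difference in change, so the SD of change matters: SD² = 1.15² + 1.10² − 2ρ(1.15)(1.10), with ρ the correlation between baseline and follow-up. Assume a 0.8 difference in change between arms (that is, no change under home exercise), equal SDs of change in both arms and a one-sided 5% test. Then 80% power needs ρ of about 0.48 with 26 analysed, 0.55 with 23, 0.59 with 21 and 0.63 with 19.

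The pilot gives some guidance on ρ:

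- **If p = 0.003 is a two-sided paired t-test (n = 7).** t = 4.80 and SD of change = 0.8 × √7/4.80 = 0.44, so ρ ≈ 0.92. The upper 97.5% limit of that SD is 0.44 × √(6/1.237) = 0.97 (ρ ≈ 0.63). At that limit, power is 80% with 19 analysed, 84% with 21 and 90% with 26.
- **If p is one-sided.** t = 4.15, SD of change 0.51, ρ ≈ 0.90. The upper limit is 1.12 (ρ ≈ 0.50), and power is 69%, 73% and 81% with 19, 21 and 26 analysed.

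**The case against.** **19 may be an enrolled number.** With 25% loss, 14/0.75 = 18.7, which rounds up to 19. On that reading 80% and 1.32 are right and only a label is missing. This is plausible, but the text gives no such rate and presents 19 as the sample size behind the power. The sentence needs rewording on either reading.

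**26 is not an arithmetic error.** The SAP allows exceptions to two-sided testing and names Aim 2 as one, and the one-sided power at 26 exceeds 80%. At 25 it is 79.8%, or 80.8% by the normal approximation. This stands. What remains is that sidedness is unlabelled in the sample-size text and that drop-out is claimed as covered but not quantified.

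**A raw-SD t-test is not the planned analysis.** The mixed model uses every participant with at least one observation, and multiple imputation is planned as a sensitivity analysis. Adjustment for baseline would lower the correlations needed to roughly 0.3, 0.4 and 0.5 with 23, 21 and 19 analysed. This is why no true shortfall is claimed. But a participant with only a baseline value adds little to a contrast of change, the plan's wording can be read as adjusting for baseline only if the groups are imbalanced, and no correlation is declared.

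**The pilot inference is fragile.** Agreed: the test behind p = 0.003 is not named, and the cohort is seven people without a control arm. It shows that a high correlation is possible; it does not establish one.

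**Conclusion.** The concern holds. As written, the n=19 statement does not follow from the plan's own inputs: its source is missing from Aim 1, and its power is 91.0% or 95.4% rather than 80%. The error understates power and does not set enrolment.

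The figure of 26 for d = 0.711 stands only as a one-sided 5% t-test on raw SDs, with essentially all 26 analysed. On that basis it leaves no real allowance for the drop-out it is also said to cover. Whether Aim 2 would actually fall short depends on the correlation between baseline and follow-up and on the loss rate, and the plan states neither.

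This is a reporting correction that should be made. It does not affect the primary endpoint, the enrolment target or the choice of test.

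**What to change.** Restate the Aim 2 paragraph on one basis, the one-sided test the SAP names, with its 5% level written out.

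1. **First statement.** Use 14 analysed per group, per Aim 1, with a detectable difference of 1.16 (or 1.32 if labelled two-sided). Alternatively keep 19, state where it comes from, and give 0.99 (or 1.12 if labelled two-sided).
2. **Second statement.** Give the assumed drop-out, the analysed number, the power at that number, and which SD is used (1.2 or about 1.125). Either label it an endpoint t-test on raw SDs (81% with 26 analysed, 77% with 23, 73% with 21, at SD 1.125), or base it on the planned contrast. Suggested wording for the latter: *Of 26 enrolled per group we assume [x]% drop-out, leaving [n] analysed; with an SD of change of [s] (correlation [rho]), one-sided 5% power for a 0.8 difference in change is [y]%.*
3. If the pilot is used to support the correlation, name the test behind p = 0.003 and present the correlation as an assumption.

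The cost is rewording only. The sponsor must declare a drop-out rate and, if the change contrast is used, a correlation.

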b. Secondary measures: Posture (other): will be calculated from the 30s duration of quiet standing data including COP ellipse area, velocity, and sample entropy[38]. In particular, the non-linear measure of sample entropy[38,51–54] may provide additional information regarding complexity of postural control regulation among cancer survivors with neuropathy. **Balance:** is a critical measure of clinical impact. The Timed Up-and-Go test, or **TUG**, (<2 min to administer) is a timed test of a person's ability to stand from a chair, walk 10 feet, turn around, and return to sitting with shorter times indicating better functional

balance. While our data indicate some clinical tests are not sensitive to chemotherapy-induced neuropathy state (e.g., Berg), Wampler et al (2007); Marshall et al. (2017); and Evans et al. (2019) reported that TUG time distinguished cancer survivors with neuropathy (n=20, 8, & 20 survivors respectively) from age-matched controls. **Patient-reported outcomes (PROs):** are critical secondary measures that will help us to understand participant perception of change with intervention. These will be collected 2x/week during multiple baseline testing then monthly thereafter with a subset captured per session to evaluate within-session effects. We will administer PROs during multiple baseline and monthly testing through retention. CIPN-20 and BPI instruments will be administered to complement one another: the CIPN 20 focuses on the effect of neuropathy symptoms on functional capacity while the BPI assesses pain symptoms. We will also collect the symptom inventory from the Sports Concussion Assessment Tool (SCAT). Additionally, we will document cancer-related fatigue (CRF), quality of life (SF-36), satisfaction with intervention, likelihood of recommending the intervention to a friend with neuropathy (this will be included as a question on the satisfaction with intervention survey), perceived benefit, intrinsic motivation, depression/apathy/ anxiety (PRO-CTCAE), and adverse events including falls. **Falls:** each participant will use a diary format to report daily changes in falls, symptoms, use of assistive devices, and amount of concurrent medication use during the study period. These factors will also be recorded by research staff within adverse event reporting 2x per week before Tango lessons. For 6 months after intervention completion, we will collect falls incidence weekly from participant daily dairy records.

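### The primary RMSml model gives concurrent medication no time point, and adjusts for covariates according to observed imbalance, in a form that would not adjust the primary contrast

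*Combined protocol and SAP*

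**What the plan says.** The Aim 1 paragraph of the Statistical Analysis Plan (Section IV.F) specifies a linear mixed model for RMSml: "Fixed effects will be included for time, treatment, treatment-by-time interactions, and concurrent medication use". Within-person correlation is handled in this way: "Random effects for subjects will be used to account for correlation between observations from the same subject". The target is stated: "The primary estimand will be a difference-in-difference representing the difference in mean RMSml change from baseline to week 16 between treatment groups".

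The covariate sentence opens "While we expect balance between the two groups due to randomization". It then lists potential confounders to adjust for: baseline RMSml, age, body mass index, and "concurrent medications (e.g., duloxetine) and other variables if imbalance between groups occurs by chance". No imbalance criterion is given. Neither mention of medication has a coding or a time point, and no covariate-by-time term appears.

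Medication data are described under Falls in Section IV.D (Aim 1, secondary measures): "each participant will use a diary format to report daily changes in falls, symptoms, use of assistive devices", and also the "amount of concurrent medication use during the study period". Staff record the same items before Tango lessons.

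The same strategy carries over to the patient-reported outcomes: "Similar analyses will be performed for the PROs sensory symptoms (CIPN-20), pain (BPI-SF" and others. Section IV.F also commits to intention-to-treat analysis unless otherwise noted.

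**The concern.** The time point of the medication variable decides what the term does, and the plan does not give it.

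- **On-study value.** The arm may influence it: a participant whose symptoms ease may take less. Conditioning on it yields an effect with recorded medication held fixed, not the total difference in change that the plan names as its estimand.
- **Baseline value, as a main effect.** The primary contrast is a within-person change compared between arms. A quantity that is constant within a person drops out of it.

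The second point applies equally to age, body mass index and baseline RMSml if each enters as a main effect in the stated model. The plan evidently wants to correct chance imbalance, and in this form it would not. Because entry depends on imbalance that nobody has defined, and the list ends in an open category, the final model is also not fixed before the data are seen.

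The on-study issue is most direct for pain and CIPN-20, where symptom-driven changes in medication are most plausible.

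**Working it through.** **Inputs from Section IV.F:** preliminary RMSml 7.9 falling to 4.6 mm, planning SD 2.7, 14 per group for 85% power, 26 per group enrolled, two-sided 5%. **From Section IV.C:** four baseline assessments, one mid and one post. **Assumed, not in the documents:** random intercept, categorical time, within-person correlation r (0.5 unless varied), and all medication rates and effects.

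**1. The plan's own figure.** d = (7.9 − 4.6)/2.7 = 3.3/2.7 = 1.22. The two-sample t-test needs 13.06, so 14 per group, as stated (power 87.5% at 14). At 26 per group, power is 99.1%.

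**2. Baseline main effect, complete data.** With time, arm and their interaction in the model, the fitted mean for arm a at time t is ȳ(a,t) − β·x̄(a), up to a common constant. The covariate part is the same at baseline and at the end, so it cancels:

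DiD = [ȳ(T,end) − ȳ(T,base)] − [ȳ(H,end) − ȳ(H,base)], whatever β is.

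Simulated mixed models agree: the largest change was 5e-14 mm, with an SE ratio of 1.000.

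**3. The same with dropout.**
- 27% or 46% dropout: mean absolute shift 0.03 to 0.07 mm, maximum 0.23 mm.
- 7 of 26 per arm lacking mid and post data, at random: 95th percentile of the absolute shift 0.07 mm.
- The same number, with dropout depending on the covariate in opposite directions by arm: mean 0.12 mm, 95th percentile 0.19 mm.

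**4. On-study value.** Now the covariate mean varies with time, and the cancellation leaves a remainder:

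shift = −g·d, where g is the fitted medication coefficient and d is the between-arm difference in change in recorded use.

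Illustrations with 40% use at baseline in both arms:

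| Final use, Tango vs HEX | g (mm) | d | −g·d (mm) | Simulated (mm) |
|---|---|---|---|---|
| 40% vs 40% | −1 | 0 | 0 | 0.00 |
| 20% vs 40% | −1 | −0.20 | −0.20 | −0.23 |
| 10% vs 50% | −2 | −0.40 | −0.80 | −0.81 |

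In these rows medication truly lowers sway. If use also tracks sway at the visit, g can be positive: g = 1.35 and d = −0.197 give a shift of +0.27, from −3.31 to −3.04. Over a grid of 20% or 30% versus 40% use, true medication effects of −1, 0 or +1 mm and visit-level correlations of 0 to 0.4, a true −3.30 became anything from −3.47 to −2.82. With no treatment effect on sway and no medication effect, rejection was 4.9 to 6.0% in five of six settings and 8.2% in the strongest, against 4.7 to 5.7% unadjusted.

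**5. When a main effect does contribute.** If baseline means are constrained equal, or post is regressed on mean baseline, the contrast is the post difference minus k times the baseline difference, with k = 4r/(1 + 3r) for four baselines. At r = 0.5, k = 2/2.5 = 0.80, so a fraction 1 − k = 0.20 of any covariate-related imbalance remains for a main effect to act on. Simulated with a covariate correlated 0.5 with sway, adding its main effect moved the constrained-model estimate by up to about 0.25 mm (95th percentile 0.15). In an ANCOVA the figures were up to 0.70 mm (95th percentile 0.28).

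**6. Gain from always handling baseline RMSml.** The ratio of residual variance to change-score variance is (1 + 4r)/[1.25(1 + 3r)]:
- r = 0.3: 2.2/2.375 = 0.926
- r = 0.5: 3.0/3.125 = 0.960
- r = 0.7: 3.8/3.875 = 0.981

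The saving is about 2 to 7%.

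**The case against.** The strongest defence is that the covariate sentence speaks of randomisation and chance, which points to baseline values. Baseline medication would cause no bias, and the primary test has ample power. That stands: harm through the on-study route needs both the on-study reading and an arm difference in medication change, and the documents give no rates or effects from which to size it.

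Five stronger readings are tempting, and the documents do not support them.

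- **The two medication sentences are incompatible.** If the imbalance condition attaches only to the final open category, medication is simply an always-included covariate named twice. The two phrases could also mean overall use and specific drugs. The text is ambiguous, not shown to be contradictory.
- **Baseline covariates matter only with by-time terms.** This holds only while baseline stays an outcome with a free treatment effect. Step 5 shows that main effects contribute once baseline means are constrained or conditioned on.
- **The written plan inflates false positives by a known amount.** Such a figure would need by-time terms and selection of the smallest p-value. The plan states neither; its trigger is imbalance. In the stated model with complete data, choosing among baseline main effects changes nothing.
- **Baseline medication is not collected.** The measurement list in Section IV.C omits it, but it omits age and body mass index too.
- **Medication is recorded more completely in the Tango arm.** The extra staff recording is tied to Tango lessons, but every participant keeps the diary and Section IV.C describes weekly check-ins with everyone.

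Always handling baseline RMSml is partly an efficiency preference, and its gain is small. It also has a second purpose: it removes a data-driven choice about the most important covariate.

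**Conclusion.** The concern holds as a specification fault that should be corrected, not as a threat to the primary result. As written, the medication term may be a post-randomisation adjustment that departs from the intention-to-treat estimand, or a baseline main effect that adjusts nothing. The zero in the second case is algebraic for complete data; with the dropout examined, the average shift was at most about 0.12 mm. The shift in the first case is zero if use does not differ by arm, and otherwise rests wholly on assumed values (0.2 to 0.8 mm in the tabulated examples, in either direction across all settings tried). Power is 99.1% at 3.3 mm and still 95.8% at 2.82 mm, the smallest effect in the step 4 grid. The imbalance-triggered, open-ended list is a weakness whatever the time point, because it defers the choice of model until after the data are seen. The sample size is unaffected.

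**What to change.** Pre-specify one primary model in Section IV.F.

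1. Omit medication from it, or include only the pre-randomisation value, with definition and coding stated once. Report on-study medication descriptively by arm.
2. Always handle baseline RMSml, either by constraining baseline means to be equal across arms in the mixed model that uses all available data, or by an ANCOVA-type model.
3. Replace the imbalance trigger and the open category with a fixed, named list of pre-randomisation covariates. Under either model in (2), main effects are enough for them to contribute. By-time terms are needed only if the unconstrained difference-in-difference model is kept.
4. Apply the same rules to the patient-reported outcome models.

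The cost is SAP wording and a check that pre-randomisation medication is recorded in both arms. No extra participants or visits are needed.

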Prospective 1:1 block randomized study, with random block sizes. Two arms: experimental and active control (Fig 1).

B. Sample

Individuals with breast cancer-related neuropathy will be recruited for this study using the following inclusion and exclusion criteria.

Inclusion criteria:

- Breast cancer survivors \geq 40 years old
- Symptomatic for neuropathy (CIPN20 sensorimotor score < 95 on transformed scale (100 maximum));
- postural control outside 70% CI for adults who are middle-aged without neurotrauma [20]);
- having completed taxane-based chemotherapy treatment at least 3 months ago;
- able to understand and comply with directions associated with testing and study treatments.

Exclusion criteria:

- Pre-existing vestibular deficit;

[figure not shown]

Fig1: Study design flowchart. TP = Testing timepoint.

- poorly controlled diabetes (hgA1C \geq 8);
- non-ambulatory or lower extremity amputation (assistive devices allowed);
- use of cytotoxic therapy during study (immune- and endocrine therapy allowed);
- participation in physical therapy during the study;
- contraindication to participate in Tango due to orthopedic issue (e.g., herniated vertebral disc);

In addition, survivors who are screened and found eligible to participate in this RCT will be asked to invite a companion to enroll with them in the study arm that the survivor is randomized into. (n=up to 100 companions)

Finally, up to 100 survivors screened who do not meet the criteria above will be offered enrollment without compensation in the intervention of their choice, along with their companion (up to n=100), as we have capacity to include them and using the “companion” consent form. Capacity will be defined based on space and staffing availability.

Therefore, in total, up to 200 survivors and up to 200 companions will be enrolled in Phase 2 of this protocol.

C. Measurement/Instrumentation

Data collected at baseline x 4, mid-intervention and post intervention (*collected at baseline x1 only):

- Adverse events (i.e., PRO-CTCAE[26], falls or loss of balance, illness or hospitalization since last visit)
- SF-36[25]
- EORTC QLQ-C30[15]
- Neuropathy symptoms: measured using original or modified forms of the EORTC CIPN-20[16]
- Sports Concussion Assessment Test (SCAT) Symptom inventory (for comparison to CIPN-20)[27,28]
- Pain: measured using original or modified forms of the Brief Pain Inventory (BPI)[29]

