Aim1: We will evaluate change in postural control over 16 sessions of Tango (exp) vs HEX (control) (n=26 per group; 1:1 randomization) as primary endpoint. As secondary measures, we will assess: balance function (i.e., TUG) and PROs (i.e., symptoms, pain, fatigue, mood, quality of life) *monthly* including 1 month post-intervention completion; postural control and symptoms *within-session*; and falls incidence *weekly for 6 months following intervention completion*. **Hypothesis:** At primary endpoint, members of the exp group will show more improvement than members of the control group in measures sensitive to neuropathy disease state (i.e., sway variability and area).

a. Primary measure: Posture (RMSml): has shown clinically relevant for future fall prediction[40–43] and neuropathy detection in cancer[44–46] and diabetes[47,48] in a host of studies. As our primary measure we will calculate this measure of medial-lateral sway variability (RMSml). Postural control (30 s duration) will be collected 2x/week during multiple baseline testing, monthly thereafter for HEX, and before and after each session for the Tango group. Center of pressure (COP) data will be recorded (1000 Hz) as participants stand quietly on a level, static balance platform (Bertec Corp, Columbus, OH) with eyes closed (QEC). As in past work[20,38,44–46], we will collect 30 second (s) of COP data and interpret these data with regard to healthy within-subject variability as defined in a middle-aged cohort [20].

RMSml will be calculated (as described by Prieto[49]) as the root-mean-squared value of COP excursion in the medial-lateral direction (mm), a formula which effectively returns the standard deviation from the mean. All data will be captured using custom software written in LabView (National Instruments, Austin, TX, US). Our team ([name], [name]) has pioneered the biomechanical assessment of balance deficits associated with cancer treatment and neurorehabilitation [20,38,44–46]. Using center-of-pressure (COP) measures captured with portable force platform equipment, we have quantified the balance dysfunction that accumulates with cancer treatment sessions (Fig 1) [1,46,50] and identified a potential effect of Tango to remediate these effects[38]. Finally, in order to translate this quantified measurement paradigm to clinical care of individuals, we published normative measures of within-subject variability (WSV) [20] to enhance our interpretation of treatment effects.

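### The SAP sets the primary RMSml contrast at week 16, but Aim 1 defines the primary endpoint over 16 sessions, which on the only lesson rate inferable from the text end at about week 8 to 10

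*Combined protocol and SAP*

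**What the plan says.** In section IV.F, under the Statistical Analysis Plan for Aim 1, the primary estimand is a difference-in-difference: the "difference in mean RMSml change from baseline to week 16 between treatment groups".

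Section IV.D counts sessions instead. The Aim 1 primary endpoint is "change in postural control over 16 sessions of Tango (exp) vs HEX (control"), and Aim 2 likewise concerns "change in gait variability after 16 sessions of Tango (exp) vs HEX (control").

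The timing of tests is given without week numbers:

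- Section IV.C: "Data collected at baseline x 4, mid-intervention and post intervention". Force-plate sway, including its variability, is on that list with no restriction by arm.
- Section IV.D, primary measure: after baseline, RMSml is taken "monthly thereafter for HEX, and before and after each session for the Tango group".
- Section IV.D, secondary measures: TUG and patient-reported outcomes are monthly, "including 1 month post-intervention completion".

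The only legible Phase 2 text that bears on lesson frequency is in the falls paragraph of section IV.D, where staff record events "within adverse event reporting 2x per week before Tango lessons". Section IV.C separately requires adverse events to be collected ahead of each session.

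**The concern.** The primary estimand and the primary endpoint use different clocks, and the legible text neither converts one to the other nor states when week zero is. If sessions run twice a week, week 16 is not the end of training. It is a point well after it, beyond even the 1-month follow-up.

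This changes the question being answered. A contrast at the end of training asks whether a course of Tango improves sway more than home exercise. A contrast weeks later asks how much of any gain is kept. Aim 1 poses the first question. An analyst following the SAP literally would answer the second, or would have to choose the visit that stands for week 16, possibly after seeing data. On the same reading, the text names no Tango RMSml test at week 16, because after baseline that arm's RMSml collection is described by session and at the post-intervention visit.

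**Working it through.** **Inputs**

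- Estimand time point: week 16 (section IV.F).
- Course: 16 sessions (section IV.D, Aims 1 and 2).
- Lesson rate: 2 per week. This is an inference. Section IV.D has adverse events recorded twice a week before lessons, and section IV.C has them recorded before every session, so twice-weekly recording implies two sessions per week.
- Baseline period: 4 tests (section IV.C) at 2 per week (section IV.D), so 4 / 2 = about 2 weeks.
- One month: 52 / 12 = 4.33 weeks (assumption).

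**Can week 16 be reproduced as the end of training?** Weeks of training = sessions / sessions per week.

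- At 2 per week: 16 / 2 = 8 weeks, not 16. Conversely, 16 weeks at 2 per week would hold 32 sessions, not 16.
- Rate needed for session 16 to fall at week 16, counting from the first session: 16 / 16 = 1 per week.
- Rate needed counting from the first baseline test: 16 / (16 - 2) = 1.14 per week.
- No legible Phase 2 text gives either of these rates.

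**Where week 16 falls at 2 sessions per week**

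| | Week zero = first session | Week zero = first baseline test |
|---|---|---|
| End of 16 sessions | 8 | 8 + 2 = 10 |
| 1-month post-intervention test | 8 + 4.33 = 12.3 | 10 + 4.33 = 14.3 |
| Week 16 minus end of training | 8 weeks | 6 weeks |
| Week 16 minus 1-month test | 3.7 weeks | 1.7 weeks |

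On either choice of week zero, week 16 comes after both the end of training and the 1-month test.

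**Is the sample size affected?** No. The section IV.F figures give d = (7.9 - 4.6) / 2.7 = 1.22. A two-sided t-test at 5% with 85% power needs 13.1 per group, rounded up to 14 (power 87.4% at 14). The stated n = 14 is reproduced, and no calendar week enters the calculation.

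**The case against.** The strongest reply is that the link may exist where we cannot see it. The caption "Fig1: Study design flowchart. TP = Testing timepoint" belongs to a figure that is not shown, and that figure is the natural place for a course length and visit weeks. This stands: the finding is limited to the legible text. A timeline in the figure would still leave the SAP sentence and Aim 1 stating the time point in different units.

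A second reply is that week 16 is simply a slip for session 16. The matching number makes this plausible. If so, the remedy is small, but the primary estimand is still misstated as written. Session 16 alone would also not fix the comparator's visit, since home-exercise participants are tested monthly.

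A third reply is that a calendar time point suits intent-to-treat better than a session count, because some participants will not reach session 16 and training may be asynchronous. This is right, and the fix adopts it.

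A reader might also infer more than the documents support:

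- **That the single mid-intervention label confirms an 8-week course.** It does not. Section IV.C gives a count for baseline but none for mid-intervention, and its list omits the 1-month test, so visits cannot be counted from it.
- **That Phase 1 confirms two sessions per week.** Its 20 sessions with testing at 5 and 10 weeks would give 20 / 10 = 2 per week, but Phase 1 also describes a 6-week intervention, so it does not settle the rate.
- **That the model would extrapolate beyond the data.** That needs a continuous time term, and the SAP does not say whether time is continuous or categorical.
- **That no RMSml test exists at week 16.** Monthly testing in the home-exercise arm has no stated end, and the figure is unseen, so absence cannot be confirmed.

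**Conclusion.** The point holds. The SAP states the primary time point as week 16, Aim 1 states it as 16 sessions, and the legible text does not reconcile them. On the only lesson rate that can be inferred, week 16 falls 6 to 8 weeks after training ends and about 2 to 4 weeks after the 1-month post-intervention test. Followed literally, the primary analysis would estimate retention instead of the change Aim 1 defines.

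The size rests on two assumptions: two sessions per week, inferred from adverse-event recording and not from an intervention schedule, and week zero at either the first session or the first baseline test. Confidence is medium for that reason and because the flowchart is not shown. The mismatch itself does not depend on the rate. It is more than missing detail, because a stated rule of the primary analysis would target a different question, and it should be settled before analysis.

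**What to change.** Reconcile the test schedule in section IV.C, Aim 1 and the falls paragraph in section IV.D, and the estimand in section IV.F, against the design flowchart.

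Unless the sponsor confirms that an RMSml test at week 16 in both arms is intended, restate the primary estimand as the between-arm difference in mean RMSml change from baseline to the post-intervention test that section IV.C already schedules. Define that test by one calendar window, counted from a stated week zero and common to both arms, so that participants who do not complete all sessions are still assessed under intent-to-treat. Treat any later RMSml test as secondary.

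The cost is one sentence of SAP wording, with no added visits or patients. If the sponsor instead confirms week 16, the schedule must name an RMSml test at that time in both arms, which may add a visit. No session frequency is proposed here.
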